**Table 8: Treatment regimen and tablet allocation**

Treatment Arm	IMM-124E Dose (600mg tab)	Regimen	Tablet allocation per dose	
			IMM-124E	Placebo
A	600mg three times daily	2 tablets (1 from each bottle) taken three times daily on an empty stomach	IMM-124E	Placebo
B	1200mg three times daily		IMM-124E	IMM-124E
C	matching placebo three times daily		Placebo	Placebo

#### 8.4.2 Supply, Packaging and Labeling, Storage and Handling

IMM-124E must be stored in a secure area with access limited to the pharmacist and authorized staff. The bottles and outer packaging will be stored refrigerated between 2 and 8 degrees Celsius, prior to dispensing to patients, in a controlled and monitored facility.

At a minimum, the immediate packaging will include the following information:

- Sponsor name
- Protocol number
- Pack/treatment number
- Product name/drug code
- Number of tablets
- Directions for use, including route of administration
- Batch/lot number
- Storage conditions
- Period of use (use by, expiry or retest date, as applicable, in month/year format)

Additional information and specific cautionary statements will be included according to local law.

The packaging lot numbers will be recorded on the investigational product accountability record.

A Pharmacy reference manual containing detailed information regarding the storage, dispensing and accountability of IMM-124E will be provided as a separate document.

#### 8.4.3 Dispensing and Accountability

The investigator will be responsible for ensuring accurate records are maintained for all study medications dispensed and returned. The inventory must be available for inspection by the study monitor. Study drug supplies, and the dispensing logs, must be accounted for by the study monitor and returned to the drug repository for destruction at the end of the study.

When requested in writing by the Sponsor, used and/or unused study medication supplies may be destroyed by the investigator provided such disposition can be performed safely. Records shall be maintained by the investigator of any such alternate disposition of the study medication. These records must show the identification and quantity of each unit disposed of, the method of destruction (taking into account the requirements of local law), and the person who disposed of the test substance. Such records shall be submitted to the sponsor.

For additional information, please refer to the Study Reference Manual for this study.

#### 8.4.4 Dosage and Administration of Study Drugs

IMM-124E and matching placebo tablets may be either chewed before swallowing or swallowed whole three times daily per oral on an empty stomach. No intra-subject dose adjustment of IMM-124E will be allowed during this study.

Range of +/- 15% (85-115%) is the acceptable compliance range.

Any poor compliance out of this range will be considered as protocol deviation.

Any poor compliance should be escalated to Immuron and will potentially result in subject's termination from the study.

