### 11.2 Criteria for Premature Withdrawal from Treatment or the Study

Subjects have the right to withdraw from treatment or the study at any time for any reason. The investigator must make every reasonable effort to keep each subject in the study except where termination or withdrawal is for reasons of safety. The investigator also has the right to withdraw subjects from treatment or the study in the event of intercurrent illness, AEs, pregnancy, treatment failure after a prescribed procedure, protocol violations, administrative reasons or other reasons.

The reasons for withdrawal of the subject must be recorded on the CRF.

The following are also considered justifiable reasons for subject withdrawal:

- The need to take medication which may interfere with study measurements
- Intolerable/unacceptable adverse experiences (see [Section 10.7](#))
- Major violation or deviation of study protocol
- Non-compliance of subject with protocol
- Subject unwilling to proceed and/or consent is withdrawn
- Withdrawal from the study is, in the investigator's judgment, in the subject's best interest
- Pregnancy of female study subject at any time during the study period (if applicable)

It is understood by all concerned that an excessive rate of withdrawals from the study can render the study difficult to interpret. Therefore, unnecessary withdrawal of subjects from the study should be avoided.

Immuron may also decide to stop the study and withdraw all subjects for safety or other reasons.

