### 11.3 Withdrawal of Subjects from Study drug

[Section 10.6](#) provides guidance for dose discontinuation of Study drug in the event of AEs or abnormal laboratory values. If a subject permanently discontinues study drug, for example as a result of an AE, subjects should be encouraged to continue participation in the study in order to obtain ongoing measurement of study outcomes to minimize missing data. At a minimum, every attempt should be made to continue to follow the subject until resolution of the adverse event. All subjects who discontinue study medication dosing should be followed for at least 28 days after the last dose of Study drug in order to monitor subjects for possible post-treatment events which may occur after Study drug has been discontinued.

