7.2 Primary efficacy analyses

The hepatic fat fraction will be summarised and tabulated for the Baseline and Week 24 visits along with change from Baseline by randomised treatment group. Change in hepatic fat fraction from Baseline will be analysed using analysis of variance on the ITT, PP and FAS populations, where the model will include the treatment group and another subgrouping variable. As determined by baseline values, hepatic fat fraction categories ($\leq 10\%$, $>10\% - <21\%$, $\geq 21\% - <30\%$ and $\geq 30\%$), HbA1c group ($< 6\%$ and $\geq 6\%$), and ALT (greater or less than 1.5 x the upper normal limit) will be used to subgroup the analysis populations. Further, data from liver biopsies up to 6 months prior to screening will also be used to subgroup analysis populations based on fibrosis (0-1 vs. 2-3), NAS inflammation (0-1 vs. 2-3), and NAS ballooning (0-1 vs. 2). These will be used in addition to the main effects factors and the two-way interaction of those main effects.

In the primary analysis, any missing data will remain missing. Treatment effects between placebo and each of the active treatment groups within each of the hepatic fat and HbA1c categories will be generated and tested for significant differences between treatment and placebo using pre-specified contrasts.

To examine the effect of treatment within the various levels of these subgroup variables, a mixed models ANOVA will be employed if there are an appropriate number of observations in each cell (created by the crossing of study treatment and subgroup categories) and the data does not differ significantly from a normal distribution. In the event that this is not the case, the data will be ranked in an attempt to normalise it, and pairwise contrasts between treatment groups will be performed using Wilcoxon rank sum tests within each combination of visit and subgroup variable level will be performed. However, if the ranked data is also not normally distributed, a permutation test will be employed whereby the unranked data will be randomly sampled (Lehmann, 2006). No adjustment for multiple testing will be made. See Appendix 1 for more information on both the Wilcoxon rank-sum test and the permutation test.

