Sensitivity analyses will be performed in the final study analysis and will use the same analysis method on the FAS and PP populations using the multiple imputation and analysis method to impute missing values and, finally, an analysis using the full set of ITT population data, but including study centre as an additional main effect.

Interaction effects with study centre will not be investigated. If any outliers are detected (defined as greater than ± 2 SD away from the mean for that group and visit combination), sensitivity analyses will be performed where those outliers are removed and then will be compared with the analysis where those outliers were not taken out.

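### Ending study participation for poor compliance can create informative missing Week 24 MRIs, and it pulls against the protocol's own retention rules

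*Protocol*

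**What the plan says.** Protocol 8.4.4 sets the standard: "Range of +/- 15% (85-115%) is the acceptable compliance range". Intake outside it is a protocol deviation, is reported to the sponsor, and "will potentially result in subject's termination from the study". The object is the study, not only the study drug.

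Protocol 11.2 speaks both ways. Near its start it says: "The investigator must make every reasonable effort to keep each subject in the study except where termination or withdrawal is for reasons of safety". Its list of reasons that justify withdrawal nevertheless includes "Non-compliance of subject with protocol". It also warns that too many withdrawals make the trial hard to interpret.

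Protocol 11.3 covers subjects who stop drug permanently: "subjects should be encouraged to continue participation in the study in order to obtain ongoing measurement of study outcomes to minimize missing data".

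Protocol 11.5 replaces early withdrawals until the planned number of completers is reached. Protocol 7.2.9 and the combined W24/WD column of Table 1 schedule a liver MRI at early withdrawal from treatment. The MRI footnote to Table 1 allows two weeks either side of Week 24.

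SAP 7.2 states: "In the primary analysis, any missing data will remain missing". Sensitivity analyses in the final analysis repeat the method "using the multiple imputation and analysis method to impute missing values". SAP 3.1 restricts the PP set to subjects with 85-115% compliance and MRIs at Baseline and Week 24.

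**The concern.** How much a subject takes is decided after randomisation and may depend on the arm, through tolerability or perceived benefit. Protocol 10.7 expects altered bowel movements and nausea as the most common reactions, and these could plausibly affect tablet-taking. If poor compliers leave the study, their Week 24 MRI is missing or taken early. An analysis that omits missing values then compares the better compliers in each arm.

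The PP set already exists to exclude non-compliers. If they also drop out of the FAS, the two sets move closer together. Agreement between them then says less about robustness, and the comparison as randomised is weakened on the primary endpoint.

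**Working it through.** **1. The rules side by side.**

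| Subject | Rule | Consequence |
|---|---|---|
| Has permanently stopped drug | Protocol 11.3 | Encouraged to stay for outcome measurement |
| Still on drug, taking for example 80% of tablets | Protocol 8.4.4 | May be terminated from the study |
| Any subject | Protocol 11.2, opening text | To be kept in the study, safety being the only stated exception |
| Non-compliant with the protocol | Protocol 11.2, list | Withdrawal is justifiable |

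Sections 8.4.4 and 11.3 do not cover the same subjects. Read together, however, someone who takes nothing is to be retained, while someone who takes most of the tablets may be removed.

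**2. From termination to the analysis.** The endpoint is the change at Week 24. A scan at withdrawal may fall well outside the two-week MRI window, and the SAP gives no rule for it. If it does not count, the value is missing and is not imputed in the primary analysis. Multiple imputation appears only as a sensitivity analysis in the final analysis, and no method is specified for data missing not at random.

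**3. The plan's own figure.** Protocol 12.1 assumes an SD of 6 at each time point and a correlation of 0.25. The SD of change is √(6² + 6² − 2 × 0.25 × 6 × 6) = √54 = 7.35, stated as 7.3. With 40 per arm, a difference of 5 points and two-sided alpha 0.05, the exact t calculation gives 85.7% power (85.2% with SD 7.35). The stated figure of about 85% reproduces. It assumes 40 evaluable subjects per arm; the synopsis says that dropouts were not allowed for.

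**4. Illustrative bias.** The documents give no rate of poor compliance or termination, so the inputs here are assumptions. A fraction q of an active arm is terminated, the retained subjects have the planned effect of 5 points, and the terminated subjects have effect b. Placebo losses, if any, are unrelated to outcome.

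Effect in all randomised = 5(1 − q) + bq. Complete-case estimate = 5.

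| q | b | All-randomised effect | Excess (points) | Overstatement |
|---|---|---|---|---|
| 10% | 0 | 4.5 | 0.5 | 5/4.5 = 1.11, 11% |
| 20% | 0 | 4.0 | 1.0 | 5/4.0 = 1.25, 25% |
| 10% | 2.5 | 4.75 | 0.25 | 5/4.75 = 1.05, 5% |
| 20% | 2.5 | 4.5 | 0.5 | 5/4.5 = 1.11, 11% |

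**5. Illustrative false-positive rate.** Suppose there is no true overall effect and the lost active subjects are g points worse than those retained. The retained subjects then look better than the whole arm by qg. With SD 7.3, 40 placebo subjects, and 36 or 32 active subjects, the two-sided rejection rate is:
- g = 5: 6.0% at q = 10% and 8.8% at q = 20%;
- g = 2.5: 5.2% and 5.9%.

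**6. Numbers.** If 10% or 20% were lost at random from both arms and not replaced, 36 or 32 per arm would give 81.7% or 76.9% power. Protocol 11.5 does provide for replacement, so this loss does not follow from the plan. Replacement restores the count but not comparability, because a terminated non-complier is exchanged for a completer.

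**The case against.** The strongest reply is that the clause is discretionary. Termination is only a possibility, after referral to the sponsor. Investigators and sponsor clinical staff are blinded (Protocol 8.2), and every arm takes the same number of tablets. Section 11.2 discourages unnecessary withdrawal, its heading covers withdrawal from treatment or from the study, and its list does not say which is meant or mention 85-115%. An MRI is scheduled at early withdrawal, and Protocol 11.4 asks for a full final evaluation. Multiple imputation is planned, SAP 8.6 examines early terminations, and the trial is an exploratory Phase 2 study.

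Much of this stands, and it rules out several stronger readings that a reader might infer:
- That the sections flatly contradict each other. They cover different subjects, and 11.2 itself supports both sides; this is a tension to be reconciled.
- That informative missingness will occur. The documents show only that it can.
- That the arms shrink to 36-32. Section 11.5 replaces withdrawals.
- That the FAS and PP sets become nearly identical. The PP set has other exclusions, and SAP 6 and its table list tabulate compliance in bands from under 50% to over 115% for the ITT, FAS and PP sets, so non-compliers are expected to remain in the analysis sets.
- That the bias is 11-25%. That range needs every terminated subject to have had no benefit, although the rule also reaches someone at 84% or above 115%.

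The reply does not remove the core. Blinded decisions do not stop treatment from influencing compliance, the withdrawal scan has no stated role in the analysis, and the planned imputation includes no missing-not-at-random method.

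**Conclusion.** The point holds in a limited form. The protocol permits termination from the study for poor compliance, in tension with its own retention rules. Because the primary analysis leaves missing outcomes missing, using that permission can produce treatment-related gaps in the primary endpoint and draw the FAS towards the PP set.

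The size in this trial cannot be computed from the documents. The overstatement of 11-25% is a worst case that assumes 10-20% termination in an active arm with no benefit; at half benefit it is about 5-11%. If the clause is rarely used, the effect is small. The direction is not fixed either, since it depends on who is terminated in each arm. The change is still worth making, because it protects the primary endpoint at little cost.

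**What to change.** - **Protocol 8.4.4, 11.2 and 11.3:** reconcile them. State that compliance outside 85-115% is recorded as a deviation and handled through the PP set, and does not by itself end study follow-up.
- **Follow-up:** whatever is decided about study drug, on which no view is taken here, still seek the scheduled Week 24 MRI and laboratory visit.
- **SAP 7.2:** state how an MRI taken at early withdrawal is used, including whether and when it may stand as the Week 24 value.

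The cost is mainly wording. Week 24 scans are already scheduled, but a subject scanned at withdrawal might need a second scan, and keeping poor compliers in follow-up takes some site effort. The FAS estimate may also be smaller.

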## 9. CONCURRENT MEDICATIONS AND TREATMENTS

At each study visit or contact, the Investigator should question the subject or their legal representative about any medication taken, including vitamin supplements and herbal remedies. Any concurrent medications will be recorded in the subject's records and the CRF. Any changes in doses or introduction of new medications during the course of the study will also be recorded.

### 9.1 Special Dietary Requirements

There are no special dietary requirements.

### 9.2 Concurrent Medications/Treatments Not Permitted

#### 9.2.1 Prior to Study Entry

Refer to Exclusion Criteria in [Section 6.3](#).

#### 9.2.2 During the Study Dosing Period

Throughout the study medication dosing period, subjects may not receive any of the following concomitant medications:

- other anti-NASH therapy(s) including, SAM-e, betaine, milk thistle and probiotic supplements (not including yoghurt);
- thiazolidinediones (glitazones), dipeptidyl peptidase 4 inhibitors (gliptins) or GLP-1 analogs, unless the subject was recruited on a stable dose.
- Allowable anti-diabetic treatment includes insulin, metformin and/or sulfonylureas administered at constant dose for at least 2 months prior to study entry;
- immune modulatory agents including
  - systemic steroids for more than 7 days
  - multiple non-steroidal anti-inflammatory drugs such as aspirin (>100mg/day), ibuprofen, naproxen, meloxicam, celecoxib;
  - azathioprine, 6-mercaptopurine, methotrexate, cyclosporin, anti-TNF $\alpha$  therapies (infliximab, adalimumab, etanercept) or anti-integrin therapies (namixilab).

Treatment with antilipidemic agents (HMG Co-A reductase inhibitors – “statins”), vitamin E, gemfibrozil and allowable antidiabetic treatment (metformin and/or sulfonylurea) must be stable throughout the study.

Antibiotics should be taken if clinically indicated but avoided where possible.

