### 3.4.2 IMM-124E Composition

IMM-124E is hyperimmune bovine colostrum that is lactose- and fat-reduced. IMM-124E is harvested from the colostrum of dairy cows which have been immunized against the outer antigens, mostly LPS, of the most common strains of Enterotoxigenic *Escherichia coli* (ETEC). This inoculation activates a generalized immune response in the host animal to produce antibody clones which recognize and bind with the bacterial cell-surface epitopes presented. These polyclonal antibodies can also cross-react with other similar bacterial cell surface antigens.

IMM-124E contains approximately 40% IgG in the drug substance, mainly IgG1 and IgA, with small amounts of IgM and IgE. The non-specific nature of the immunoglobulins in IMM-124E and high binding activity against the LPS moiety of ETEC and non-ETEC gram-negative bacteria facilitates the potential for broad protective coverage against these infective agents.

Immuron's IMM-124E-based product, Travelan, has been sold in Australia over-the-counter (for use by adults and children over 6 years of age) at a dose 200 mg three times a day since September 2004. Approximately 140,000 packets (30 tablets each packet) have been sold and no treatment-related adverse events have been reported.

For more information on IMM-124E, please refer to the current Investigator's Brochure

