#### 3.5.1.2 Safety Dose Modeling

IMM-124E is well tolerated in clinical studies and in the market place. While the typical dose for traveler's diarrhea is 600mg/day, doses as high as 10g four times daily have been studied. Adverse reactions have been few in number and mild in severity. In most clinical studies of bovine colostrum, there have been no treatment related adverse events reported and no clear pattern in events [Tacket *et al.*, 1992; Shield *et al.*, 1993; Mitra *et al.*, 1995; Sarker *et al.*, 1998; Huppertz *et al.*, 1999; Opekun *et al.*, 1999].

Adverse events observed include:

- nausea, flatulence [Rump *et al.*, 1992; Plettenberg *et al.*, 1993]
- nausea and vomiting in 1/24 patients [Greenberg and Cello 1996]
- mild diarrhea in 1/8 adult volunteers [Lissner *et al.*, 1998]

Tacket *et al.* (1988) reported no adverse clinical signs, but transient moderate elevations in serum levels of hepatic transaminases in volunteers who received bovine immunoglobulin concentrates prepared against *E. coli* (5/10) and rotavirus (2/10). This effect was attributed to diets high in protein provided at the hospital. Colostrum administration should be avoided in person allergic to cow's milk or with lactose intolerance.

The known safety profile of bovine colostrum gives a substantial therapeutic index. Therefore, the highest dose to be evaluated will be 3600mg/day.

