## 14. Concurrent medications including:

- Anti-NASH therapy(s) taken for more than 10 continuous days in the last 3 months. These include S-adenosyl methionine (SAM-e), betaine, milk thistle, bacterial probiotic supplements (other than yoghurt or other natural food sources), vitamin E and gemfibrozil.
  - NOTE: If determinant biopsy is performed while on stable treatment – subject is eligible;
  - Wash out for any of the anti-NASH therapies is as follow: under 10 days no washout required, more than 10 days and up to 3 months treatment requires 6 weeks washout. Any treatment of over 3 months would require to re-biopsy to ensure histological eligibility
  - Thiazolidinediones (glitazones), dipeptidyl peptidase 4 inhibitors (gliptins) or glucagon-like peptide-1 analogs in the last 6 months.  
NOTE: if determinant biopsy is performed while on stable treatment of at least 6 months – subject is eligible.
  - NOTE: Allowable anti-diabetic treatment includes metformin and/or sulfonylureas administered at constant dose for at least 2 months prior to study entry
  - NOTE: Subjects treated with Insulin are eligible if clinically stable on insulin treatment (i.e. no recurrent acute hypo-/hyperglycemic episodes diagnosed clinically and by Glucose serum levels of <50 mg/dL and >200 mg/dL respectively) for at least 2 months prior to study entry
- immune modulatory agents including:
  - Within 3 months of study entry:
    - systemic steroids for more than 7 days
    - daily treatment with multiple non-steroidal anti-inflammatory drugs (such as aspirin >100mg/day, ibuprofen, naproxen, meloxicam, celecoxib) for more than 1 month
  - In the last 12 months:
    - azathioprine, 6-mercaptopurine, methotrexate, cyclosporin, anti-TNF $\alpha$  therapies (infliximab, adalimumab, etanercept) or anti-integrin therapies (namixilab)
- more than 10 consecutive days oral or parenteral antibiotics within 4 weeks prior to study entry NOTE: subjects administered with antibiotics for more the 5 days prior to study entry would not be included in the stool and PBMC analysis)
- Variable dose of anti-lipidemic agents (HMG Co-A reductase inhibitors – “statins”) in the 3 months prior to Screening

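### The marketed form of the study drug, and other bovine colostrum products, are not named in the entry or prohibited-medication lists, so their use is not clearly barred

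*Protocol*

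**What the plan says.** **The marketed product.** Protocol 3.4.2: "Immuron's IMM-124E-based product, Travelan, has been sold in Australia over-the-counter", "at a dose 200 mg three times a day since September 2004". On volume: "Approximately 140,000 packets (30 tablets each packet) have been sold". Three doses of 200 mg make 600 mg a day, the amount that Protocol 3.5.1.2 ties to another use: "While the typical dose for traveler's diarrhea is 600mg/day". The trial arms take 1800 mg (Arm A) and 3600 mg (Arm B) a day.

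**Entry.** The anti-NASH item of exclusion 14 (Protocol 6.3) is spelled out: "These include S-adenosyl methionine (SAM-e), betaine, milk thistle, bacterial probiotic supplements (other than yoghurt or other natural food sources), vitamin E and gemfibrozil". Exclusion 17 concerns allergy, lactose intolerance and hypersensitivity, not use. Section 9.2.1 only points back to the exclusions, and section 9.1 sets no dietary rule.

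**During dosing.** Section 9.2.2 bars "other anti-NASH therapy(s) including, SAM-e, betaine, milk thistle and probiotic supplements (not including yoghurt", certain antidiabetic classes, and "immune modulatory agents including" steroids, anti-inflammatory drugs, immunosuppressants and biologics. No colostrum or oral immunoglobulin product appears.

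**Provisions that bear on it indirectly.** Section 9 has sites ask about and record all medication, supplements and herbal remedies at every visit. Section 11.2 accepts a need for interfering medication as grounds for withdrawal. SAP 3.1 lets the medical monitor designate, before lock and unblinding, deviations that could distort the results. The SAP has no rule specific to colostrum products.

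**The concern.** The lists go down to milk thistle and probiotics but pass over the one product that contains the agent under test. The sponsor markets it, so the route was known when the lists were drawn up. One subject in three receives placebo, the study title identifies the agent as bovine colostrum, and blinding the tablets does not stop anyone buying a similar product.

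Three things are at stake:

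- **Placebo arm.** Use shrinks the primary contrast, the Week 24 change in liver fat against placebo.
- **Arm A.** A user at the marketed dose would take 1800 + 600 = 2400 mg a day. That narrows the gap to Arm B from 1800 to 1200 mg and blurs the comparison behind the objective of establishing a recommended dose.
- **Before the Baseline MRI.** Use could lower the Baseline value, move a subject to another fat-fraction stratum and leave less change to measure. Because it precedes randomization, it should be balanced across arms in expectation. It attenuates change rather than favoring an arm.

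**Working it through.** **1. Is use clearly barred?**

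| Provision | Does it settle the matter? |
|---|---|
| Anti-NASH item (6.3 no. 14; 9.2.2) | Open list, but the documents link the marketed daily amount to traveler's diarrhea, not NASH |
| Immune modulatory item (9.2.2) | Open list, but the examples are all of a different kind |
| Exclusion 17 | No: hypersensitivity only |
| Recording at each visit (9) | Captures reported use; does not forbid it |
| Withdrawal for interfering medication (11.2) | Discretionary, and only after exposure |
| Compliance (SAP 6) | Counts dispensed study drug only |
| Serum sampling (Protocol 12.7) | Concentrations are not expected, so undisclosed use need not show |
| Major violations (SAP 3.1) | Case by case, for the medical monitor to judge |

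Several provisions could be stretched to cover use. None names it.

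**2. The plan's own power (Protocol 12.1).** Inputs: 40 per arm, difference 5 points, SD 7.3, two-sided alpha 0.05, unpaired t-test.

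- SD of change = sqrt(6² + 6² − 2 × 0.25 × 6 × 6) = sqrt(54) = 7.35; the protocol uses 7.3.
- Noncentrality = 5 / (7.3 × sqrt(2/40)) = 5 / 1.632 = 3.063, on 78 degrees of freedom.
- Power = 85.7% (86.5% by the normal approximation). The stated figure of about 85% reproduces.

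**3. Dilution.** Let c be the share of placebo subjects using the product throughout and f the share of the planned effect they gain. The difference becomes 5 × (1 − c × f), with the SD held at 7.3. The documents give neither c nor f. For f, one third is the dose ratio 600/1800, which assumes that effect is linear in dose. The value 1 is the ceiling if users gain no more than the planned effect.

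| c | Difference, f = 1/3 | Power | Difference, f = 1 | Power |
|---|---|---|---|---|
| 0 | 5.000 | 85.7% | 5.00 | 85.7% |
| 5% | 4.917 | 84.5% | 4.75 | 82.0% |
| 10% | 4.833 | 83.3% | 4.50 | 77.7% |
| 20% | 4.667 | 80.6% | 4.00 | 67.7% |

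Allowing for the extra spread from mixing users and non-users lowers the one-third figures by less than 0.2 points (at 20%, 80.61% becomes 80.45%).

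**4. How demanding are these scenarios?** Assume 200 mg tablets.

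- Marketed dose for 24 weeks: 3 × 168 = 504 tablets, about 17 packets of 30.
- Matching Arm A's daily amount: 1800/200 = 9 tablets a day, 9 × 168 = 1,512 tablets, about 50 packets.
- One packet at the marketed dose lasts 10 days. Scaled by time and dose (assumption), it yields (10/168) × (1/3) = 2% of the effect. At 20% use power would still be about 85.4%.
- Total sales: 140,000 × 10 days = 1.4 million treatment days, about 3,800 person-years. If cumulative from September 2004 to May 2016 (assumption, about 11.7 years), that averages about 330 users at any time.

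**The case against.** The strongest reply is that this is a small wording gap with safeguards around it. Both list items are open-ended. In this trial IMM-124E is itself the anti-NASH therapy under test, and Protocol 3.4.1 and 3.5 describe colostrum as acting on the immune system. Section 8.4.4 allows no change of IMM-124E dose within a subject. Reported use is on record before lock, and the examples of major violations in SAP 3.1 are not exhaustive. Sale is reported only in Australia, site countries are not listed, and the trial calls itself exploratory.

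Much of this stands, and it rules out three stronger readings that a reader might draw:

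- *A subject could take the product with no deviation, and the per-protocol set could not remove that subject.* The open lists and the medical monitor's discretion mean only that use is not clearly a deviation.
- *Power could fall to 67.7%.* That needs 8 of 40 placebo subjects to gain the full effect from a product whose marketed dose is one third of Arm A's.
- *140,000 packets show wide exposure.* Spread over the years on sale, they do not.

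What the reply does not remove is ambiguity. A site applying 9.2.2 to a product not described as a NASH treatment has no firm answer, and two sites may decide differently. Recording lets use be examined afterwards but does not prevent it.

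**Conclusion.** The gap is real on the text: use of the marketed product, or of any other bovine colostrum product, before the Baseline MRI or during dosing is not clearly barred. Placebo-arm use would bias the primary contrast towards zero.

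The size is probably small. With sustained use at the marketed dose and one third of the effect, the loss is 1.2 points of power at 5% use, 2.4 at 10% and 5.1 at 20%. Occasional short courses would cost almost nothing. The full-effect figures are an upper bound on the loss at each uptake, not an expectation. All of these rest on assumed uptake and assumed linearity in dose.

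Nothing in the documents shows that contamination occurred. The patient information sheet and the Study Reference Manual were not available, so a restriction there cannot be excluded. The case for change rests on a foreseeable route and a near-free remedy, not on a large expected loss.

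**What to change.** - Name *Travelan or any other bovine colostrum or bovine immunoglobulin product* in exclusion 14 (synopsis and Protocol 6.3) and in section 9.2.2.
- List its use among the deviations reviewed as major for the per-protocol set under SAP 3.1, decided before unblinding. Identify users from the concurrent-medication question already asked at each visit (Protocol 9).
- State whether the existing anti-NASH duration and washout terms in exclusion 14 are meant to apply to it. That is for the sponsor to settle.
- If the patient information sheet or Study Reference Manual already carries a restriction, align the protocol wording with it.

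The cost is one line in each list at the next amendment and one line in the SAP. A very small number of candidates may become ineligible. No visits or tests are added, and the planned power of 85.7% is unchanged.
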